8.2 Recording Adverse Events and Serious Adverse Events

Adverse events (AEs) will be evaluated and documented by the clinical staff and investigators throughout inpatient hospitalizations and each outpatient visit. CRAs are responsible for reviewing documentation related to AEs and entering directly into TrialMaster protocol-specific database. The data to be recorded are 1) the event description, 2) the NCI CTCAE v4.0 code and grade, 3) the onset date, 4) the resolution date (or ongoing), 4) action taken for event, 5) patient outcome 6) relationship of AE to protocol treatment/interventions, 7) if AE was expected or unexpected, and 8) comments, if applicable.

AEs that are classified as serious, unexpected, and at least possibly related will be notated as such in the database as “unanticipated problems”.

Attribution of an Adverse Event

Not related – The lack of a temporal relationship of the event to study treatment makes a causal relationship not reasonably possible, or other drugs, therapeutic interventions or underlying conditions provide a sufficient explanation.

Unlikely related – The temporal relationship of the event to study treatment makes a causal relationship reasonably unlikely, and other drugs, therapeutic interventions or underlying conditions may not provide sufficient explanation for the observed event.

Possibly related – The temporal relationship of the event to study treatment makes a causal relationship reasonably possible, and the event is more likely explained by exposure to the study treatment than by other drugs, therapeutic interventions or underlying conditions.

A cumulative summary of all non-hematologic Grade 3-5 AEs, and expected/unrelated deaths that occur more than 30 days after protocol treatment will be reported to all sites with study progress report at the time of continuing review.

For the purpose of safety analyses, all AE's that are classified as unlikely or possible will be considered treatment-related events.

8.3 Process for Reporting Adverse Events To and From St. Jude and Collaborating Sites/Affiliates

Adverse events from collaborating sites will also be reviewed by the PI and discussed in study team meetings as described above. SAE reports from collaborating sites for AEs that are serious, unexpected, and at least possibly related to protocol treatment or interventions will be reported to site IRB and the St. Jude IRB within the reporting requirements described above. The PI will determine if this is an event that will need to be reported expeditiously to all participating sites, considering the following criteria:

- Is the AE serious, unexpected, and related or possibly related to participation in the research?
- Is the AE expected, but occurring at a significantly higher frequency or severity than expected?
- Is this an AE that is unexpected (regardless of severity that may alter the IRB's analysis of the risk versus potential benefit of the research *and*, as a result, warrant consideration of substantive changes in the research protocol or informed consent process/document?

With the submission of the "Reportable Event" in St. Jude iRIS application, the PI will indicate if all sites should be notified to report to their IRBs, and if the protocol and/or consent should be amended (consent will be amended if event is information that should be communicated to currently enrolled subjects). Generally, only events that warrant an amendment to the protocol and/or consent will be reported expeditiously to all sites. However, any event may be reported expeditiously to all sites at the discretion of the PI. A cumulative summary of all non-hematologic Grade 3-5 AEs, and expected/unrelated deaths that occur more than 30 days after protocol treatment will be reported to all sites with study progress report at the time of continuing review.

For collaborating sites: Serious AND unexpected events are to be reported to the St. Jude PI ([name]) within 48-72 hours via fax or email.

All treatment-related deaths and unexpected deaths must be reported to the St. Jude PI at HYPERION study team by e-mail or phone call to [name] within 24 hours of the event. A written report must follow.

The study team should be copied on all correspondence regarding the event. Sent report to:

[name]
Department of Oncology
Leukemia/Lymphoma Division
St. Jude Children's Research Hospital
[name]
[name]
Phone: [REDACTED]
FAX: [REDACTED]
Email: [REDACTED]
Email: [REDACTED]

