Intensive Low End Target (mmHg)	110						
Intensive High End Target (mmHg)	120						

Patients will begin antihypertensive therapy to achieve the targeted blood pressure on Day 4 of Remission Induction on TOT17. Patients already receiving antihypertensive therapy prior to Day 4 should have their therapy adjusted according to the guidelines below.

During outpatient visits, blood pressures measured should be performed after the patient has been sitting at rest for at least 10 minutes and is not experiencing pain or anxiety.

During induction, blood pressure adjustments will be made for each patient based on the mean blood pressure over the preceding 4 days (minimum 2 measurements) unless indication for immediate change is met (listed below). Blood pressures obtained while a patient is sedated for procedures should not be included in the evaluated blood pressures when determining whether to adjust antihypertensive medications. Patients with mean blood pressures outside of the target range should have antihypertensive therapy adjusted in an attempt to reach the goal range. However, if prior changes to medication have been made within 7 days and blood pressures are both 1) closer to the target range than at the time of prior medication change and 2) within 10mmHg of the goal range following that change, further modifications can be delayed until a subsequent visit.

Immediate changes to antihypertensive therapy are indicated if:

- 1) systolic pressures are more than 15mmHg above the high end target,
- 2) patients are experiencing headache, vision changes, or neurologic symptoms attributable to hypertension,
- 3) the patient has experienced an episode of syncope,
- 4) the patient's systolic pressure is below 90, or
- 5) the patient is experiencing unacceptable toxicity from their current antihypertensive therapy.

Patients will continue antihypertensive therapy (as needed to achieve the targeted blood pressure range) during phases of therapy with scheduled glucocorticoids (i.e. Induction and Continuation, including Reinduction 1 & 2). Patients should continue antihypertensive therapy during other phases if tolerated. Caution is warranted in consolidation (due to the risk of altered renal perfusion or kidney injury) and during immunotherapy (due to the risk of cytokine release induced hypotension).

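### The attribution scale in 8.2 sets too high a bar for *Possibly related* and leaves a gap, so adverse events with a competing cause can leave the treatment-related count and relatedness-triggered reporting by open-label judgement

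*Combined protocol and SAP*

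**What the plan says.** Section 8.2 defines three attribution levels.

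- *Not related*: either the timing rules out a causal link, or, as a separate and sufficient condition, "other drugs, therapeutic interventions or underlying conditions provide a sufficient explanation".
- *Unlikely related*: the timing "makes a causal relationship reasonably unlikely, and other drugs, therapeutic interventions or underlying conditions may not provide sufficient explanation for the observed event". Both parts must hold.
- *Possibly related*, the highest level: the timing makes a causal link reasonably possible, and "the event is more likely explained by exposure to the study treatment than by other drugs, therapeutic interventions or underlying conditions".

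Attribution then acts as a filter in three places.

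- Safety analyses (end of 8.2): "all AE's that are classified as unlikely or possible will be considered treatment-related events".
- Unanticipated problems (8.2): "AEs that are classified as serious, unexpected, and at least possibly related will be notated as such in the database".
- Forwarding of collaborating-site reports to the site IRB and the St. Jude IRB (8.3): the trigger is "AEs that are serious, unexpected, and at least possibly related to protocol treatment or interventions".

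The Protocol Summary describes the trial as unblinded and states blinding only for the radiologist who reads the MRIs. No blinded attribution of adverse events is provided for.

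**The concern.** The harms that intensive blood pressure control could add are the ones that chemotherapy and infection also cause. The Protocol Summary names postural hypotension and creatinine rises as the anticipated risks. Section 2.2 says anemia and infection may predispose these patients to symptomatic hypotension. Section 4.1 adds: "Caution is warranted in consolidation (due to the risk of altered renal perfusion or kidney injury". Competing explanations are therefore to be expected for many of the events of interest.

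A scale whose top level requires the study treatment to be the more likely cause will not reliably capture such events. The judgement is made by people who know the arm, so it can differ between arms. Randomisation already supplies the background rate of toxicity, so comparing the arms needs no case-by-case causal judgement. Section 10 nevertheless plans no between-arm comparison of adverse events, and every row of the 10.8 table is marked N under Safety. The only stated rule for classifying events in safety analyses is the attribution rule in 8.2.

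**Working it through.** **Step 1. Apply the 8.2 definitions to each combination of timing and alternative cause.**

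| Timing | Alternative cause | Level under 8.2 | Treatment-related in safety analyses | At least possibly related |
|---|---|---|---|---|
| No temporal relationship | Any | Not related | No | No |
| Link unlikely | Sufficient | Not related | No | No |
| Link unlikely | May not be sufficient | Unlikely related | Yes | No |
| Link plausible | Sufficient | Not related | No | No |
| Link plausible | Not clearly sufficient, but as likely as the study treatment or more so | None | Undefined | Undefined |
| Link plausible | Not clearly sufficient, and less likely than the study treatment | Possibly related | Yes | Yes |

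Two faults follow. The fifth row has no level. The ordering is also incoherent: a poorly timed event in the third row counts as treatment-related, while a well-timed, confounded event in the fourth row does not and one in the fifth row has no assured place. Counting *Unlikely* events does not rescue the confounded ones, because *Unlikely* is defined by poor timing.

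**Step 2. List where attribution is not a filter.**

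- 10.3 counts acute kidney injury by grade and duration, and syncope by whether injury resulted. The only stated limit is to glucocorticoid-containing phases.
- 9.1 records non-hematologic grade 3-5 events in those phases and provides toxicity summaries at least monthly to the PI and Biostatistics.
- 8.2 and 8.3 send sites a cumulative summary of non-hematologic grade 3-5 events.
- 8.3 has collaborating sites report serious and unexpected events to the PI with no relatedness test.
- 8.1 says, in a separate sentence, that the principal investigator must report all serious adverse events to the FDA and IRB. This does not agree with the relatedness condition stated elsewhere in 8.1 and in 8.2 and 8.3.

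**Step 3. Why 10.3 should be explicit.** The 8.2 sentence speaks of safety analyses in general, so someone could carry its filter into the 10.3 count. An exact three-look binomial recursion on the 10.3 boundary (more than 7/20, 13/40, 25/80) at a true rate of 0.35 gives suspension probabilities of 0.399, 0.217 and 0.177. The plan states 0.40, 0.22 and 0.18. The unrounded total is 0.79. Suppose, as an assumption, that attribution removed 25% or 50% of events:

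- 25%: the counted rate is 0.35 × 0.75 = 0.2625 and the total is 0.128 + 0.070 + 0.049 = 0.25.
- 50%: the counted rate is 0.35 × 0.50 = 0.175 and the total is 0.02.

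The rule as written applies no such filter. The figures show only what would be lost if one were read into it.

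**Step 4. Illustration for a between-arm count.** No rate here comes from the documents, and the plan contains no such test. Take 180/2 = 90 per arm and assumed true rates of 20% (intensive) and 10% (standard). If a fraction f of events is classed *Not related*, the counted rate is the true rate × (1 − f). Two-sided 5% power is approximately Φ[(d − 1.96·SE₀)/SE₁], where d is the difference in rates, SE₀ the pooled standard error and SE₁ the unpooled one.

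- f = 0: 20% v 10%, (0.10 − 1.96 × 0.0532)/0.0527 = −0.08, power 47%.
- f = 50% in both arms: 10% v 5%, (0.05 − 1.96 × 0.0393)/0.0391 = −0.69, power 25%.
- f = 80% in both arms: 4% v 2%, (0.02 − 1.96 × 0.0254)/0.0254 = −1.18, power 12%.
- f = 50% in the intensive arm only: 10% v 10%, difference 0.
- f = 50% in the standard arm only: 20% v 5%, difference 15 points.

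Equal filtering dilutes a real difference. Unequal filtering can erase or inflate it.

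**The case against.** The strongest reply is that the harm most at issue is already handled. Acute kidney injury is a named targeted toxicity in 10.3, counted without a relatedness condition, and the channels in step 2 keep confounded events in view. The 8.2 rule is also inclusive on its face, since it leaves out only *Not related*. Expectedness is a separate filter: postural hypotension and transient creatinine rises are already listed as anticipated, so a looser attribution definition would not by itself make them expedited reports.

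Much of this stands, and it rules out some stronger readings that a reader might infer.

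- *Any kidney injury with a competing chemotherapy cause is classed as not related.* The text does not say so. That level needs the alternative to be a sufficient explanation. An alternative that is merely present or equally likely leaves the event without a level.
- *Such events drop out of safety analysis altogether.* They do not, for the reasons in step 2.
- *Only events at least possibly related reach the IRB.* The sentence on all serious adverse events in 8.1 contradicts this.
- *The consolidation warning in 4.1 shows the filter at work.* It shows that competing renal causes are foreseen. But 4.1 gives the scheduled-glucocorticoid phases as Induction and Continuation, so kidney injury in consolidation is outside the 10.3 count and the 9.1 recording sentence because of phase. Rewording 8.2 would not bring it in.

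The reply does not remove the fault. The 10.3 rule watches one arm against a fixed rate, does not compare arms, and covers hypotension only through syncope with injury. The unfiltered summaries are not a planned analysis by arm.

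**Conclusion.** The scale in 8.2 is defective as written: its top level is too strict, *Not related* overrides plausible timing, and one class of confounded event has no level. As a result such events can leave the treatment-related safety count and the reporting that relatedness triggers, through judgements made with knowledge of the arm. The loss is confined to those uses.

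The size cannot be derived from the documents, which give neither toxicity rates by arm nor the share of events with a sufficient alternative cause. The power figures rest wholly on assumed rates and losses and describe no planned test. The conclusion about the definitions needs no numerical assumption. It assumes only that staff apply 8.2 as it reads. The change should be made, because it is cheap and removes a potentially biased filter on the harms that intensive control could add.

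**What to change.** 1. In 8.2, define *Possibly related* as plausible timing where the study treatment cannot be excluded, even if other causes are also plausible. Narrow *Not related* to match, so that the three levels together cover every event.
2. Replace the last sentence of 8.2 with: *Safety analyses compare the randomised arms on all recorded adverse events regardless of attribution; attribution is used for reporting only.*
3. State in 10.3 that targeted toxicities count regardless of attribution.
4. Reconcile the relatedness condition on reporting in 8.1, 8.2 and 8.3 with the sentence in 8.1 that all serious adverse events are reported to the FDA and IRB.

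The cost is wording in four sections and one adverse event table by arm. Somewhat more events will be labelled possibly related, and those that are also serious and unexpected will add to reporting.

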9.0 DATA COLLECTION, STUDY MONITORING, AND CONFIDENTIALITY

9.1 Data Collection

Electronic case report forms (e-CRFs) will be completed by the clinical trials staff from the Cancer Center Comprehensive Center, Hematological Malignancies Program. Data will be entered from record directly into a secure, protocol-specific TrialMaster database, developed and maintained by St. Jude Clinical Research Informatics.

Data Management will be supervised by the Director of Clinical Trials Management, and Manager of Clinical Research Operations for the Hematological Malignancies Program, working with [name] or his designee. All protocol-specific data and non-hematologic grade 3-5 adverse events during glucocorticoid phases will be recorded by the clinical research associates into the protocol-specific database, ideally within 2-4 weeks of completion of study phase. Osteonecrosis (CTCAE Grade 2 or higher) will be recorded. All questions will be directed to the attending physician and/or PI and reviewed at regularly-scheduled working meetings. Data collection for adverse events will be captured for 4 weeks after participant is removed from treatment.

The attending physicians (or their designees) are responsible for keeping up-to-date roadmaps in the patient's primary St. Jude medical chart. Regular (at least monthly) summaries of toxicity and protocol events will be generated for the PI and the department of Biostatistics to review.

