Brief Outline of Treatment Plan: Patients will be randomized on day 4 of induction therapy to either conventional or intensive blood pressure goals. Patients will be treated with the long-acting antihypertensive lisinopril to achieve blood pressure control as indicated by their randomized arm. Long-acting therapy will be adjusted every 3-4 days as needed to achieve targeted control based on the median of blood pressures obtained in that period. Treatment of hypertension to the target will continue until the completion of reinduction II therapy. Patients will be evaluated for osteonecrosis as indicated in their primary therapeutic protocol using MRI during reinduction II.
Study Design: Randomized unblinded trial of conventional vs. intensive hypertensive control. Evaluation of the MRIs defining the primary endpoint will be performed by a blinded radiologist.
Sample Size: We will randomize 160 evaluable patients (180 total).
Data Management: Data management and statistical analysis will be provided locally by the Comprehensive Cancer Center Hematological Malignancies Program and the Biostatistics Department at St. Jude Children’s Research Hospital.
Human Subjects: The risks to subject will be related to the toxicity of antihypertensive therapy. Side effects are anticipated to be mild and limited to reversible orthostatic/postural hypotension and transient increases in creatinine. Patients will be informed of this and other minor side effects during informed consent discussion. Adverse events will be monitored and reported and treated appropriately.

TABLE OF CONTENTS

1.0	OBJECTIVES	1
1.1	Primary Objective	1
1.2	Secondary Objectives	1
1.3	Exploratory Objectives	1
2.0	BACKGROUND AND RATIONALE	2
2.1	Background	2
2.2	Rationale	2
2.3	Background and Rationale for Ancillary and Exploratory Studies	3
3.0	RESEARCH PARTICIPANT ELIGIBILITY CRITERIA AND ENROLLMENT	4
3.1	Inclusion Criteria	4
3.2	Exclusion Criteria	4
3.3	Research Participant Recruitment and Screening	5
3.4	Enrollment on Study at St. Jude	5
3.5	Enrollment Instructions for Collaborating Sites	5
4.0	TREATMENT PLAN	6
4.1	Treatment	6
4.2	Participation of St. Jude Affiliates in the Treatment Plan	9
4.3	Treatment Modifications for Collaborating Sites	9
4.4	Supportive Care	9
4.5	Symptom Survey and Semi-structured Interviews	10
5.0	REQUIRED EVALUATIONS, TESTS, AND OBSERVATIONS	12
5.1	Pre-Study Evaluations	12
5.2	Evaluations during Therapy	12
5.3	Response Evaluations	13
5.4	Off-Study Evaluations	13

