2.2 Rationale

Based on the retrospective clinical and prospective preclinical data, undertreatment of hypertension is associated with an approximately 2-fold increased risk of developing osteonecrosis after accounting for other known risk factors. Data from both adult^{14,15} and pediatric¹⁶ populations shows a benefit to more intensive blood pressure control compared to conventional control. Due to the risks of complications from untreated hypertension (e.g. posterior reversible encephalopathy syndrome), it is both impractical and unethical to randomize patients to no treatment for their hypertension. We will therefore test the efficacy of intensive hypertensive control (targeted to the 50-75th

percentile for age, sex, and height, systolic) compared to conventional antihypertensive control (targeted to the 90-95th percentile for age, sex, and height, systolic). We have chosen slightly higher systolic blood pressure goals for the intensive arm compared to the ESCAPE trial¹⁶ due to the presence of anemia and risk for infection in pediatric ALL patients, both of which may predispose to an increased risk of symptomatic hypotension.

The Children's Oncology Group AALL0232 and CCG1961 trials demonstrated differences in osteonecrosis in patients receiving dexamethasone instead of prednisone during induction, or continuous instead of alternate week dexamethasone during delayed intensification, respectively.^{2,5} These data support the critical role that these two steroid-intensive phases of therapy (termed induction and reinduction in St. Jude Total Therapy protocols) play in the development of osteonecrosis. The planned intervention will therefore encompass these two periods.

Although TOT17 includes an optional randomization for vincristine and dexamethasone duration (49 weeks vs. 101 weeks), the primary endpoint in this study (Reinduction II MRI) occurs prior to that randomization. Thus, the randomization will not impact the primary outcome of the study. Furthermore, review of symptomatic osteonecrosis timing on TOTXVI suggests that the majority of patients develop symptoms prior to this timepoint. For secondary endpoints including CTCAE symptomatic osteonecrosis, we will consider dexamethasone duration as a covariate.

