6.2 Toxicity Evaluation Criteria

CTCAE version 4 (to coincide with CTCAE criteria used in TOT17) will be used to document all toxicities which occur on study.

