10.3 Monitoring

To monitor the safety of therapy intensification, we will monitor for the following targeted toxicities: acute kidney injury (CTCAE grade 3 or higher not resolving to grade 0-1 within 72 hours) and syncope resulting in any injury. We will count events occurring during glucocorticoid containing phases only.

The intensive BP control arm (experimental) will be closely monitored for adverse effects and clinically suboptimal efficacy. The monitoring rules are constructed according to the Binomial group sequential design. We shall suspend the trial and investigate if any threshold defined in the rules is crossed.

AE monitoring in the intensive treatment arm: Probabilities of suspending trial to monitor > 25% targeted AE:

	True targeted AE probability			
	0.20	0.25	0.30	0.35
Suspend if number of AEs >7/20	0.03	0.07	0.23	0.40
Suspend if number of AEs >13/40	0.01	0.03	0.14	0.22
Suspend if number of AEs >25/80	0.00	0.01	0.12	0.18

Monitoring of missing the target in the intensive treatment arm: against <70% Probability of stopping

	True success probability			
	0.55	0.60	0.70	0.75
Suspend if number of successes <12/20	0.59	0.40	0.11	0.04
Suspend if number of successes <24/40	0.17	0.13	0.07	0.03
Suspend if number of failures <51/80	0.19	0.24	0.04	0.00

Efficacy monitoring of failures at reinduction II MRI (failure defined as $\geq 30\%$ involvement in any joint) against >50% failure rate.

	True success probability				
	0.35	0.40	0.45	0.50	0.55
Suspend if # successes <7/20	0.42	0.25	0.13	0.06	0.02
Suspend if # successes <16/40	0.31	0.23	0.13	0.05	0.01
Suspend if # successes <33/80	0.17	0.17	0.08	0.02	0.00

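### Section 9.1 limits adverse event entry to grade 3-5 in glucocorticoid phases, in conflict with 6.2 and 8.2; if it governs, the mild harms the plan expects go unentered, and no by-arm comparison of harms is planned

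*Combined protocol and SAP*

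**What the plan says.** The Protocol Summary, under Human Subjects, describes the expected harms: "Side effects are anticipated to be mild and limited to reversible orthostatic/postural hypotension and transient increases in creatinine". Section 2.2 explains that the intensive goals were set slightly higher than those of a cited paediatric trial because of anaemia and infection risk, "both of which may predispose to an increased risk of symptomatic hypotension".

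Three sections then govern what is recorded:

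- Section 9.1: "non-hematologic grade 3-5 adverse events during glucocorticoid phases will be recorded by the clinical research associates into the protocol-specific database". One event has a lower threshold: "Osteonecrosis (CTCAE Grade 2 or higher) will be recorded".
- Section 6.2: CTCAE version 4 "will be used to document all toxicities which occur on study".
- Section 8.2: "CRAs are responsible for reviewing documentation related to AEs and entering directly into TrialMaster protocol-specific database". The fields include the CTCAE code and grade, and no minimum grade is given.

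Section 10.3 names the targeted toxicities as "acute kidney injury (CTCAE grade 3 or higher not resolving to grade 0-1 within 72 hours) and syncope resulting in any injury", and adds: "We will count events occurring during glucocorticoid containing phases only". Its adverse event suspension thresholds apply to the intensive arm.

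Section 4.1 has antihypertensives continue in phases without scheduled glucocorticoids if tolerated, and advises caution in consolidation because of altered renal perfusion or kidney injury.

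**The concern.** The trial asks whether a lower blood pressure target is worth adopting to prevent osteonecrosis. That is a question of benefit against tolerability, in a population that need not be hypertensive to enrol (3.1.1). The harms that the plan itself expects lie below the grade at which 9.1 starts recording. The authors set an event-specific threshold for osteonecrosis, which is the efficacy outcome, but none for the expected harms of blood pressure lowering.

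If data staff follow 9.1, a reduction in osteonecrosis would be reported without a systematic account of the low-grade hypotension or creatinine change that came with it. If some sites follow 9.1 and others 8.2, low-grade data would exist but be uneven across sites. In an open-label trial they could also be uneven between arms.

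**Working it through.** The check is mainly a comparison of text. The documents state no figure for low-grade event rates, so there is none to reproduce.

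**Step 1. The recording rules side by side.**

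| Section | Grades | Phases | Arms |
|---|---|---|---|
| 6.2 | all toxicities | on study | not restricted |
| 8.2 | no floor stated | hospital stays and each outpatient visit | not restricted |
| 9.1 | 3-5, non-haematological (osteonecrosis 2+) | glucocorticoid phases | not restricted |
| 10.3 | kidney injury 3+ persisting beyond 72 hours; syncope with injury | glucocorticoid phases | suspension rule in intensive arm only |

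Sections 8.2 and 9.1 both describe the protocol-specific TrialMaster database. Nothing says which of the three recording rules prevails.

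**Step 2. Follow specific events through the rules.**

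| Event | Entered under 9.1? | Counted under 10.3? | Entered under 8.2? |
|---|---|---|---|
| Transient creatinine rise below grade 3, induction | no | no | yes |
| Postural dizziness below grade 3, no injury, reinduction | no | no | yes |
| Grade 3 kidney injury, consolidation | no (phase) | no (phase) | yes |
| Grade 3 kidney injury beyond 72 hours, induction | yes | yes | yes |

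The first two rows are the harms that the Summary anticipates. The third is the risk that 4.1 names. All three depend on which section governs. The fourth is captured on any reading.

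**Step 3. Look for another source of the same information.** Section 6.1 stores blood pressure as weekly medians in induction and one median per later phase, which does not show short hypotensive episodes. The cumulative summaries sent to sites (8.2, 8.3) are also limited to grade 3-5.

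**Step 4. Look for a planned comparison.** Sections 10.4 to 10.6 contain no between-arm analysis of adverse events. The table in 10.8 marks every listed analysis N for safety. Section 8.2 gives an attribution rule for safety analyses, but section 10 does not define any.

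**Step 5. What a comparison could show (illustration only).** Assume complete capture in all 180 randomised patients, 180/2 = 90 per arm, and a two-sided 5% test. With p̄ the mean of the two rates:

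power = Φ[(|p1 − p2| − 1.96·s0)/s1], where s0 = √(2·p̄(1 − p̄)/90) and s1 = √([p1(1 − p1) + p2(1 − p2)]/90).

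- 35% vs 15%: s0 = 0.0645, s1 = 0.0628; (0.20 − 0.1265)/0.0628 = 1.17; power 0.88.
- 25% vs 10%: s0 = 0.0566, s1 = 0.0555; (0.15 − 0.1110)/0.0555 = 0.70; power 0.76.
- 20% vs 10%: s0 = 0.0532, s1 = 0.0527; (0.10 − 0.1043)/0.0527 = −0.08; power 0.47.

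Fisher's exact test gives 0.85, 0.71 and 0.40 for the same pairs. All the rates are assumptions.

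**The case against.** The strongest reply is that 8.2 is the dedicated section on recording adverse events. It has no grade floor, feeds the same database, and agrees with 6.2. Section 9.1 also provides for all protocol-specific data, and the case report form is not in the documents. This stands: low-grade capture is unresolved, not excluded.

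A reader might infer that the harms of tighter control are never counted, that the number of low-grade events in the database will be zero, or that poor tolerability would be invisible. The documents do not support any of these:

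- Even under 9.1 read strictly, grade 3-5 non-haematological events in glucocorticoid phases are recorded in both arms.
- Section 10.3 counts two serious renal and hypotensive harms against suspension thresholds in the intensive arm.
- Other signals bear on tolerability: monitoring of missed blood pressure targets (10.3), unacceptable toxicity and refusal as off-therapy reasons (7.2), adherence checks at least weekly (4.1), the between-arm blood pressure comparison (10.5), and toxicity summaries at least monthly (9.1).
- Events judged serious, unexpected and possibly related are flagged in the database under 8.2, with no phase limit stated.

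These signals do not replace by-arm counts of the expected mild harms. Adherence and target attainment do not say what symptoms occurred, and the suspension rule has no control-arm comparator.

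It can also be said that mild symptoms in an open-label trial are prone to ascertainment bias. That is true. It bears on how much weight such data carry and favours laboratory creatinine. It also argues for one uniform rule rather than leaving the conflict in place.

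**Conclusion.** The point holds in a conditional form. Section 9.1 conflicts with 6.2 and 8.2 on which grades are entered. If 9.1 governs, the mild postural hypotension and transient creatinine rises that the Summary expects are not entered as adverse events in either arm, and events in phases without glucocorticoids fall outside the routine entry rule while treatment may continue. Whichever section governs, section 10 plans no between-arm comparison of harms.

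The size of the loss cannot be derived, because the documents give no rates for these events. The power range of 0.47 to 0.88 shows only that large differences would be detectable if recorded completely, and that a doubling from 10% to 20% might well be missed. The primary analysis, sample size and blood pressure targets are not affected. The change is worth making because it is cheap and bears on how a positive result could be used.

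**What to change.** 1. Reconcile 6.2, 8.2 and 9.1 so that one rule states which grades, phases and arms are entered, and apply it at all sites.
2. In 9.1, add targeted capture in both arms, for the whole intervention period (Day 4 to completion of Reinduction II dexamethasone, including phases without glucocorticoids), of hypotension or orthostatic symptoms, syncope, and creatinine increase. Record all grades, or at least grade 2 and above.
3. In section 10, add a descriptive by-arm summary: patients with at least one such event, by grade and phase, with the difference between arms and a confidence interval. Give laboratory-based creatinine more weight than reported symptoms, because staff and patients know the assigned target. Add a matching row to 10.8.

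The cost is a few form fields and modest extra data entry. This assumes that creatinine is measured routinely during treatment and is in the chart: the protocol lists a chemistry panel at entry (5.1) and otherwise defers to the parent treatment protocol. Low-grade symptoms will remain subject to open-label ascertainment. No change to treatment, targets or the primary analysis is needed.
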